9 STATISTICS AND DATA ANALYSIS

9.1 SAMPLING

9.1.1 Sample Size

Quantitative sample size

As this is a feasibility study, no formal sample size calculation for comparative estimates has been carried out. The aims are to provide robust estimates of rates of consent, retention, and adherence to the intervention and to gain estimates of the outcome event rates to accurately inform power calculations for a future definitive trial. We aim to recruit 50 participants across two sites over a 15-month period. Allowing for 20% loss to follow up, data will be available for 40 participants. A sample size has been chosen to ensure the objectives of the study can be met.

If we identify 100 eligible patients, we will be able to estimate a consent rate of 50% to within a confidence interval of +/-10%. If 50 patients are recruited, we will be able to estimate a retention rate of 80% to within a confidence interval of +/-11%. If we obtain complete data on 40 participants, we will be able to estimate an adherence rate of 60% to within a confidence interval of +/-15%.

Nested qualitative study

We will conduct semi-structured interviews with people with MS and their carers (n=15-20), and separate interviews with clinicians (n=6-8) who supervised/delivered the intervention. Sample size is informed by the information power concept, taking account of the study's well-defined aim, focused data gathering, preparation and ongoing review to enable informative dialogue during interviews and use of case analysis in combination with previous research.⁷⁵

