7.4 STUDY DESIGN AND METHODS OF DATA COLLECTION

7.4.1 Study design

A randomised controlled feasibility study comparing SNMES plus usual care versus usual care only with a nested qualitative study.

This will involve

- 1) A randomised controlled trial comparing SNMES plus usual care (n=25) versus usual care only (n=25). Total of 50 participants.
- 2) A nested qualitative study using semi-structured interviews for people with MS who took part in either arm of the randomised controlled trial and their carers (n=15-20).
- 3) A nested qualitative study using semi-structured interviews for healthcare practitioners and staff who were involved in the set up or delivery of the study and intervention (n=6-8).

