7.4.7 Randomisation

Randomisation lists will be generated using block randomisation with random variable block length, stratified by site and MS type, and a 1:1 randomisation ratio.

Lists will be produced by an independent statistician at Liverpool Clinical Trials Centre (LCTC).

Participant allocations will be irrevocably generated upon completion of the web-based randomisation form by a delegated member of the trial research team. Allocation concealment will be ensured as the service will not release the randomisation code until the participant has been recruited into the trial; this takes place after completion of all baseline measurements.

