9.2 DATA ANALYSIS

9.2.1 Quantitative analysis

Descriptive statistics will be used to summarise data in respect to study objectives and outcome measures as outlined below.

- Estimating screening, recruitment and attrition rates.
- Collecting data on candidate outcome measures to determine the primary outcome for the future trial and enable sample size calculations based on this.
- Determining intervention acceptability.
- Evaluating the feasibility and acceptability of health economics measures.

Feasibility progression criteria

Programme criteria using a traffic light system, along with outcome measures and qualitative data will guide decisions about whether a future definitive trial is feasible and warranted and identify any required amendments.⁷⁶

Outcome	Green: feasible with minimal or no modifications	Amber: feasible with moderate modifications	Red: major modifications required/ limited feasibility.
Consent rates	>50%	30-50%	<30%

(of eligible people)			
Retention at 6 months	>80%	60%-80%	<60%
Intervention adherence	≈ 22 sessions or more	≈ 10-21 sessions	≈ 9 sessions or fewer

Health economic component

The aim of the future trial will be to determine the effectiveness and cost-effectiveness of SNMES. This study will provide preliminary data for a descriptive analysis of quality-of-life measures, main cost drivers and differences between groups. It will inform preparatory work regarding rudimentary cost-effectiveness or value of information analysis and data collection methods for resource use and economic evaluation in the definitive trial. Overall levels of data completeness will also be evaluated.

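### The ±15% precision stated for adherence counts both arms; with only the 25 SNMES participants able to adhere, the protocol's own calculation gives ±19%

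*Protocol*

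**What the plan says.** Section 9.1.1 makes no formal power calculation and rests the sample size on precision instead: "The aims are to provide robust estimates of rates of consent, retention, and adherence to the intervention". It recruits 50 people and then states: "Allowing for 20% loss to follow up, data will be available for 40 participants". Three precision statements follow: a consent rate of 50% from 100 eligible patients (±10%), a retention rate of 80% from 50 recruited (±11%), and adherence: "If we obtain complete data on 40 participants, we will be able to estimate an adherence rate of 60"%. The precision claimed for adherence is ±15%.

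Section 7.4.1 gives the arm sizes: "A randomised controlled trial comparing SNMES plus usual care (n=25) versus usual care only (n=25). Total of 50 participants". Section 7.4.7 confirms the allocation: "stratified by site and MS type, and a 1:1 randomisation ratio". Section 7.4.9 supplies the control arm with booklets and a diary, and Section 10.2 explains why controls cannot be given a device. In Section 9.2.1 adherence is a progression criterion measured in sessions, green being about "22 sessions or more". Section 7.4.8 sets the maximum at 36 sessions over 12 weeks.

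**The concern.** The quantity to be estimated is adherence to the intervention, and only people who have been given the device can adhere to it. The 40 in the adherence sentence is the number left in the whole trial, so it includes controls, who have nothing to adhere to. The denominator exceeds the number of people in the only arm that can contribute.

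Precision is the sole quantitative argument for the sample size, and adherence is the only one of the three progression criteria that concerns the intervention itself. A reader would expect a 60% estimate to come with an interval of roughly 45% to 75%, which is narrower than this design can give on the calculation used.

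**Working it through.** **Inputs**
- Assumed adherence rate: p = 0.60 (Section 9.1.1).
- Stated denominator: 50 × (1 − 0.20) = 40, both arms (Section 9.1.1).
- SNMES arm: 25 (Sections 7.4.1 and 7.4.7).
- Confidence level: not stated. I take two-sided 95%, because it reproduces all three of the protocol's figures. A 90% level gives 8.2, 9.3 and 12.7 points and reproduces none of them.

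**Formula:** half-width = 1.96 × √[p(1 − p)/n].

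**The protocol's own figures**
- Consent: 1.96 × √(0.50 × 0.50/100) = 9.8 points (stated 10).
- Retention: 1.96 × √(0.80 × 0.20/50) = 11.1 points (stated 11).
- Adherence: 1.96 × √(0.60 × 0.40/40) = 15.2 points (stated 15).

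The arithmetic is right in all three. Consent and retention also use the right denominators. Only the adherence n is wrong.

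**Adherence with the SNMES arm as denominator**

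| n | Basis | 95% half-width | Exact 95% interval |
|---|---|---|---|
| 40 | both arms after 20% loss (as stated) | 15.2 points | 43% to 75% (24/40) |
| 25 | all randomised to SNMES | 19.2 points | 39% to 79% (15/25) |
| 20 | 25 less 20%, if loss is equal by arm and also removes session data | 21.5 points | 36% to 81% (12/20) |

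For n = 25: 1.96 × √(0.24/25) = 0.192. For n = 20: 1.96 × √(0.24/20) = 0.2147.

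For scale, a half-width of 15 points at 60% needs n = 0.24 × (1.96/0.15)² = 40.98, so 41 people in the SNMES arm alone.

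**The case against.** **Could 40 be the right denominator after all?** Two phrases might suggest it. Section 7.4.9 mentions recording device use in the control booklet, and Section 9.1.2 speaks of adherence with exercise when describing sampling for the interviews. Neither helps. Controls have no device, Section 9.1.1 names adherence to the intervention, and Section 9.2.1 counts sessions. The denominator error stands.

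**Is ±19% the true precision?** Only if adherence is a proportion of participants. The green threshold is a session count, and 22/36 = 61% is close to the assumed 60%, so 60% could instead mean the average share of sessions completed. The half-width would then depend on a standard deviation that the protocol does not give. As an assumed range, an SD of 0.25 gives 1.96 × 0.25/√25 = 9.8 points and an SD of 0.35 gives 13.7 points with n = 25. On that reading ±15% would be met in the SNMES arm alone for any SD up to 0.15 × √25/1.96 = 0.38. This objection stands, and the correction has to be conditional. It does not rescue the sentence, whose figure was reached by a binomial calculation on 40 people.

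**Is ±21% the better figure?** It assumes that the 20% loss is equal in both arms and that those lost have no session data. The protocol does not split loss by arm, and its retention criterion is at 6 months, whereas sessions accrue over 12 weeks and are logged in a diary. Someone lost by 6 months may still have adherence data. Only n = 25 comes directly from the document.

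**Stronger readings that a reader might infer.** The reference to complete data could be taken to mean that adherence will be analysed in completers only, and so be biased upwards. The protocol does not say that. The phrase belongs to a precision illustration, and the criterion in Section 9.2.1 carries no such restriction. Nor is it a fault here that the protocol leaves open whether sessions are summarised by a mean, a median or a proportion reaching the threshold; a statistical analysis plan commonly settles that.

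**How much does it matter?** No progression rule uses a confidence interval, and the traffic lights guide the decision together with outcome measures and qualitative data. The sample size does not change. That limits the consequence but does not make the stated number correct.

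**Conclusion.** The point holds as a denominator error in one sentence. The stated ±15% for adherence needs 40 people who can adhere, and the design has 25. On the protocol's own binomial calculation at 95%, the half-width is ±19% (19.2 points, 4.0 more than the 15.2 that the formula gives for n = 40). It would be about ±21% (21.5 points) if only 20 SNMES participants had adherence data, under the two assumptions named above.

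The conclusion rests on a 95% level, a true rate of 60%, and adherence expressed as a proportion of participants. The consent and retention precisions are unaffected. The documents do not support going further, to a biased adherence analysis or to unsound session thresholds.

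**What to change.** Replace the adherence sentence in Section 9.1.1 with, for example:

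> Adherence will be assessed in the participants randomised to SNMES (n = 25). If adherence is expressed as the proportion of participants who adhere, a rate of 60% will be estimated to within a 95% confidence interval of ±19%.

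Neither the sample size nor the session thresholds in Section 9.2.1 need to change. I would not use this correction to redefine the traffic light as a proportion of participants: that would require new amber and red cut-offs and would be more than a wording change. The cost is one edited sentence and a less favourable stated precision, with no extra participants.

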9.1.2 Sampling Technique

Randomised controlled trial

Potential participants will be identified and screened by a researcher via attendance at routine MS clinic appointments and searching of respective unit patient databases. People with MS who meet the eligibility criteria will be provided with verbal and written information.

Nested qualitative study

We will use purposive sampling to ensure diversity in characteristics of treatment allocation (intervention vs usual care), high versus low engagement/adherence with exercise, study recruitment site and patient demographics/protected characteristics. We will also collect reasons for declining participation or stopping the intervention in the study (where possible).

9.2 DATA ANALYSIS

9.2.1 Quantitative analysis

Descriptive statistics will be used to summarise data in respect to study objectives and outcome measures as outlined below.

- Estimating screening, recruitment and attrition rates.
- Collecting data on candidate outcome measures to determine the primary outcome for the future trial and enable sample size calculations based on this.
- Determining intervention acceptability.
- Evaluating the feasibility and acceptability of health economics measures.

Feasibility progression criteria

Programme criteria using a traffic light system, along with outcome measures and qualitative data will guide decisions about whether a future definitive trial is feasible and warranted and identify any required amendments.⁷⁶

Outcome	Green: feasible with minimal or no modifications	Amber: feasible with moderate modifications	Red: major modifications required/ limited feasibility.
Consent rates	>50%	30-50%	<30%

(of eligible people)			
Retention at 6 months	>80%	60%-80%	<60%
Intervention adherence	≈ 22 sessions or more	≈ 10-21 sessions	≈ 9 sessions or fewer

Health economic component

The aim of the future trial will be to determine the effectiveness and cost-effectiveness of SNMES. This study will provide preliminary data for a descriptive analysis of quality-of-life measures, main cost drivers and differences between groups. It will inform preparatory work regarding rudimentary cost-effectiveness or value of information analysis and data collection methods for resource use and economic evaluation in the definitive trial. Overall levels of data completeness will also be evaluated.

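### Adherence is planned as a share of people but judged by a session count with no summary statistic or population, so the same data can be green or amber

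*Protocol*

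**What the plan says.** Section 9.1.1 gives the planned precision for adherence, with a stated half-width of 15 points: "If we obtain complete data on 40 participants, we will be able to estimate an adherence rate of 60" per cent. The 40 itself is derived earlier in that section: "Allowing for 20% loss to follow up, data will be available for 40 participants", that is, 50 recruited less one fifth. Section 7.4.1 splits the 50 into 25 on SNMES plus usual care and 25 on usual care only.

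The traffic-light table in section 9.2.1 sets adherence in sessions. Green is about "22 sessions or more", amber about 10 to 21, and red about 9 or fewer. The row names no summary statistic and no analysis population, and nothing in the protocol links the 60% to the session bands.

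Section 7.4.8 gives a 12-week programme building up to three or four sessions a week, capped at 36 in all. The suggested week in the same section has four session days (days 1, 2, 4 and 5). Section 10.3 says that the number of days went from three to four while the stimulation per muscle stayed the same.

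**The concern.** Adherence is one of three quantitative progression criteria, and the protocol expresses it in two units that do not convert into each other. A proportion of people says how many reached a standard. A session count, without a stated summary, could be an average, a median or a per-person threshold.

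Three consequences follow.

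- The colour depends on a choice that can still be made after the data are seen.
- If the complete-data basis of section 9.1.1 is carried over to the light, participants who drop out are left out. If they also did fewer sessions, which is likely, the figure is pushed upward.
- The precision quoted for adherence is better than the study can deliver, because usual-care participants are in its denominator.

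**Working it through.** **Inputs.** From section 9.1.1: 60% adherence, n = 40, ±15%, 20% loss. From section 7.4.1: 25 per arm. From section 7.4.8: 12 weeks, at most 36 sessions, four session days in the suggested week. From section 9.2.1: cut-offs of 22, 10 and 9 sessions. The confidence level is not stated, so 95% two-sided is assumed.

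**Step 1: reproduce the plan's figure.** The normal-approximation half-width is 1.96 × √(p(1 − p)/n).

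- Adherence: 1.96 × √(0.6 × 0.4/40) = 15.2 points, against 15 stated.
- The same formula gives 9.8 for consent (50%, n = 100; 10 stated) and 11.1 for retention (80%, n = 50; 11 stated), which supports the 95% assumption.

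The 60% in section 9.1.1 is therefore a share of participants.

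**Step 2: use the people who can adhere.**

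- All randomised to SNMES: 1.96 × √(0.24/25) = 19.2 points.
- After 20% loss, 25 × 0.8 = 20: 1.96 × √(0.24/20) = 21.5 points.

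**Step 3: where the 22 may come from.** 0.60 × 36 = 21.6, and 22/36 = 61.1%. The green line looks like 60% of the session maximum, which is a different quantity from 60% of people. The denominator is itself unclear. Three sessions a week for 12 weeks is 36, but the suggested four for 12 weeks is 48, and 22/48 = 45.8%.

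**Step 4: one adherence rate, different colours.** In each case 15 of 25 people (60%) reach 22 sessions.

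| Sessions done | Mean | Median |
|---|---|---|
| 15 do 22, 10 do 0 | 15 × 22/25 = 13.2 (amber) | 22 (green) |
| 15 do 36, 10 do 21 | (540 + 210)/25 = 30 (green) | 36 (green) |

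**Step 5: effect of leaving out drop-outs.** Illustrative arm of 25: 14 people do 36 sessions, 6 completers do 3, and 5 drop-outs do 2.

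- Completer mean: (14 × 36 + 6 × 3)/20 = 522/20 = 26.1 (green).
- All-randomised mean: (522 + 5 × 2)/25 = 532/25 = 21.3 (amber, read as about 21).
- All-randomised median: 36 (green).
- Share reaching 22 sessions: 14/20 = 70% of completers, but 14/25 = 56% of all randomised. With a 60% mark, these fall on opposite sides.

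**The case against.** The strongest reply is that the choice of summary statistic and the handling of drop-outs are commonly left to a statistical analysis plan, which may exist. The lights also only guide a decision that draws on outcome and qualitative data as well. Both points are fair, and the second limits the seriousness. But the protocol itself fixes both the rate and the threshold, in different units, so a later plan could choose a statistic without removing the mismatch. It is also true that the examples are constructed: they show that the colour can differ, not how often it would.

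Some stronger readings are tempting but not supported.

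- A reader might infer that the green lines for consent (>50%) and retention (>80%) contradict the plan, since exactly 50 of 100 or 40 of 50 would be amber. Section 9.1.1 states 50% and 80% as conditional precision assumptions, not success marks. The bands meet without gap or overlap, and only a result exactly on the line changes colour. Any cut placed at the true rate gives roughly even odds of green: 46% for consent and 44% for retention as written, 54% and 58% with the boundary included. That is a matter of preference.
- A reader might say that a mean between 21 and 22 falls in no band. The cut-offs are marked as approximate, so 21.3 reads naturally as amber.
- A reader might say that the 60% has no possible relation to the table. Step 3 shows a likely origin, though the protocol does not state it.
- A reader might say that the light itself is restricted to completers. That basis appears only in the precision sentence; the table names no population.

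**Conclusion.** The point holds for adherence only, and it should be corrected. The planned rate is a proportion of people, the light is a session count, and no statistic or population joins them, so the same data can be green or amber. The stated ±15% does not apply to adherence: at 60% the half-width is about ±19 points with all 25 SNMES participants, or ±21 with about 20. These figures assume 95% normal-approximation intervals, equal arms and 20% loss in the SNMES arm. That a completer basis flatters adherence rests on the assumption that drop-outs do fewer sessions. No change to the consent and retention boundaries is called for.

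**What to change.** In section 9.2.1, define an adherent participant as one who completes the table's green number of sessions within the 12-week programme, stated as an exact whole number. Judge the light on the proportion adherent among all randomised to SNMES (n = 25), with drop-outs counted at the sessions that they completed. Set green, amber and red limits on that proportion before data are seen. Green could be 60% if the sponsor intends the section 9.1.1 figure as the mark; the amber and red limits are for the sponsor to choose. Report the session mean and distribution as description only.

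In section 9.1.1, replace the adherence precision with about ±19 points at 60% for n = 25, noting about ±21 if only some 20 have data.

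Reconcile the 36-session maximum with the suggested four-session week over 12 weeks (48) in section 7.4.8, so that the session cut-off has a clear denominator. Which total is intended is for the sponsor to state.

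The cost is one table row and a few sentences, with no change to design, sample size or data collection. The adherence figure and its precision will look less favourable.

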9.2.2 Qualitative analysis

Analysis will be informed by Braun and Clarke's reflective thematic analysis, drawing on inductive and deductive approaches which link to previous research in people with MS, long-term diseases and use of qualitative research for informing trials.⁷⁷⁻⁸⁰

All interviews will be audio-recorded using an encrypted Dictaphone, transcribed, anonymised and checked. Data will be transcribed using University approved transcription services who are compliant with GDPR and checked by the research team to ensure transcripts are anonymised. Anonymised transcripts will be blindly coded and the data investigated by two research team members. Coding will be open and inductive. Themes and subthemes will be produced iteratively and independently. Preliminary themes will be discussed with the wider project and clinical teams for review.

Analysis may be carried out using NVivo qualitative data analysis software.

Data from people with MS, carers and healthcare staff will be analysed separately and where appropriate, we will synthesise experiences, ensuring the recognition of the respective group voices. Findings will be mapped to the TFA and be used to inform study strategies for facilitating recruitment, retention, adherence and communication in a future trial.⁸⁰

Qualitative and quantitative data will be used in combination to inform the future definitive trial design. In

addition to the frameworks above, the intervention and methodology will also be iteratively mapped to the TIDieR checklist, APPEASE framework and Health Inequalities Assessment toolkit.^{11,81,82}

Qualitative data from the interviews will be transferred from encrypted Dictaphone to a password protected computer for onward transfer to a centralised SharePoint site specific to the study and housed under the governance structure of the Sponsor. Only the relevant members of the research team will have access to the site.

Audio-recordings will be deleted from the recording device or computer as soon as they have been uploaded to the relevant site.

Archiving

[name] will have overall responsibility for study management including regular contact with the Walton and Wolverhampton research departments, study sponsor, site PIs and wider team. Walton will be the host organisation and University of Liverpool will be the sponsor. Walton will provide centralised study communications, data tracking, monitoring, and management. This is to ensure timely set up and co-ordinated running of the study, facilitated by effective communication across sites and study teams, monitoring of study process and deliverables against study milestones and outcomes. The Walton centre has a track record of recruiting and coordinating national multicentre studies in Multiple Sclerosis.

Data and all appropriate documentation will be stored for a minimum of 10 years after the completion of the study, including the follow-up period, consistent with the Data will be stored for 10-years in accordance with University of Liverpool Research Data Management policy (<https://www.liverpool.ac.uk/csd/records-management/retention-schedule/>), the UK Research and Innovation Data Policy, Data Protection Act 2018 and GDPR 2018 (unless otherwise directed by the funder/sponsor/regulatory bodies). Case report forms will be stored in locked filing cabinets at study trust sites. The anonymised study database will be managed through REDCap. After that period all hard copy material will be reviewed, and approval for destruction from the sponsor will be sought.

